19.3 Discrepancy checks

Data discrepancies that cannot be resolved by simple checking and reference to paper copies will be referred to the steering committee, blind to allocation, for discussion of a resolution.

19.4 Security and back-up of data

Once all data is entered, the database will be locked. Data will be stored on password protected systems in SLaM and KCL. The allocation database will be accessible only to the lead research worker (who will not conduct post-baseline assessments) and the CI [name] until the study is completed. Outcome data processing

PROTOCOL IDENTIFICATION Amendment number: Original V1 Issue date: 251021 Authors: [name] Amendment I 010322: Figures for feasibility amended to proportions; proportion of children giving baseline data added (as logical follow-on from parental consent/child assent rates).

will be carried out by researchers who do not have access to allocation, intervention or feedback data. After data is checked, blind to allocation, a final database will be returned to the statistician, who will combine with allocation data for analysis.

The Chief Investigator will act as custodian for the trial data. The following guidelines will be strictly adhered to:

Child/teacher data will be pseudonymised for the duration of the study and fully anonymised at the end of the study. The fully anonymised data will be kept indefinitely. Fully identifiable personal details will be kept on paper in a locked filing cabinet in a locked or occupied office; on secure Trust computers; and, encrypted, on password protected computers in the university until the end of the study (January 2023).

Pseudonymised data will be stored on personal laptop computers, using MHRN recommended encryption (Trucrypt).

All trial data will be stored in line with the Data Protection Act and archived in line with the relevant institutional policies.

20. Statistical methods

Prior to the database lock a statistical analysis plan will be developed and approved by the Trial Team.

20.1 Primary outcome analysis

The primary feasibility outcomes will be assessed by proportions, with their associated 95% confidence interval. No hypothesis tests will be carried out on these.

20.2 Secondary outcome analysis

The potential primary outcome the M&MF will be summarised using a mixed effects linear regression, fitting a random effect to explain the heterogeneity across school and class. Fixed effects will include baseline score, child sex and age. The between-group summary effect will be reported with the 95% confidence interval and intra-cluster correlation.

All other secondary outcome measures will be summarised descriptively and to show levels of completeness.

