Appendix 1: Study Synopsis

Title of clinical trial	A feasibility, cluster randomised, 16-week, parallel-group pilot study to investigate the feasibility of trial procedures for a larger multicentre comparison of a digital school-based cognitive behavioural resilience/wellbeing-building intervention ('CUES-Ed') targeting emotional and behavioural problems in vulnerable primary school children in whole classes, compared to the usual school curriculum.
Protocol Short Title/Acronym	Building Resilience in Children. The CUES-Ed research project: feasibility study.
Study Phase if not mentioned in title	Feasibility study
Sponsor name	SLaM/KCL
Chief Investigator	[name]
REC number	LRS/DP-21/22-25994
Medical condition or disease under investigation	Emotional and behavioural problems in vulnerable children (scoring at or below borderline/clinical cut-off) receiving the intervention in whole classes
Purpose of clinical trial	To investigate the feasibility of trial procedures
Primary objective	Evaluate trial procedures
Secondary objective (s)	Estimate parameters to determine sample size for a full trial Validate classroom-based outcome measure Standardise teacher adherence rating Validate child quiz
Trial Design	Parallel group cluster RCT
Endpoints	Primary endpoint: post intervention at 16 weeks
Sample Size	We plan to consent 360 children from 10 schools (each with 2 classes)
Summary of eligibility criteria	Inclusion criteria: In Year 4 of a participating school Parental consent/child assent Exclusion criteria: None
Intervention	A cognitive behavioural resilience/wellbeing building intervention, comprising seven modules with 25 learning objectives, delivered weekly to whole classes, on a digital platform, facilitated by teachers

PROTOCOL IDENTIFICATION Amendment number: Original V1 Issue date: 251021 Authors: [name]
Amendment I 010322: Figures for feasibility amended to proportions; proportion of children giving
baseline data added (as logical follow-on from parental consent/child assent rates).

	(Digital CUES-Ed CBT programme, teacher led). The intervention lasts 12 weeks. The delivery window will be 16 weeks to fit school terms. Assessments will be completed at 0, 8 and 16 weeks, within a 1-month window.
Maximum duration of treatment of a Subject	16-weeks
Version and date of protocol amendments	V1 251021

CONTENTS

ITEMS 1-5: ADMINISTRATIVE INFORMATION.....1-2

- 1. Title**
- 2. Trial registration**
- 3. Protocol version**
- 4. Funding**

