6.1.2 CUES-Ed intervention

CUES-Ed is an innovative prevention and early intervention programme rooted in evidence-based Cognitive Behaviour Therapy (CBT) and designed by Clinical Psychologists as a result of direct feedback gathered over many years from children we have worked with in Child and Adolescent Mental Health

CUES-Ed is designed for delivery to whole classes of primary-aged children (7-10 years) to ensure they learn useful ways of looking after themselves and their mental health. They are taught by clinical psychologists or CBT therapists to understand when things are not going well and develop life-long skills to help manage any difficulties now and those that might emerge later in adolescence or adulthood. While all children are expected to gain some benefit, vulnerable children within the class are the key target group for change.

Learning about mental health needs to start from an early age for it to be most effective – and we have found a way of engaging children in a creative and interactive way – with exciting, visually strong and recognisable branding and characters that promote mental health in a positive way.

Across eight whole-class sessions, children learn cognitive strategies and simple but effective behavioural techniques through fun hands-on activities that make abstract concepts more concrete and memorable.

We promote flexible and adaptive responses to difficulties, including self-regulation (the ability to monitor and manage thoughts, behaviours and emotions; especially important when things are difficult or when strong emotions take over) and support-seeking - recognising when extra help is needed. These approaches encourage children to learn the skills that can help build their resilience from an early age. The CUES-Ed workbook for children, parent newsletters, weekly home-tasks and digital development reinforce the key concepts at school and home and promote long-term retention of learning.

Feedback on CUES-Ed from teachers:

"This program has been meaningful and with a clear purpose. The impact on the children cannot be underestimated – this program has not been an 'add on', but has really started to change the attitudes of the children."

"All the children have been able to access the course. They have learned strategies and vocabulary to help them. They have become more confident in recognising and talking about their feelings and are applying their strategies in class, the playground and at home."

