7.1 Trial Objectives

Aims: We plan to test the feasibility of our trial procedures for a subsequent study evaluating the effectiveness of the CUES-Ed intervention, as an adjunct to the usual school curriculum, compared to the usual school curriculum alone, in reducing emotional and behavioural problems in vulnerable Year 4 schoolchildren in England, receiving the intervention as part of a whole class.

Feasibility will be judged as being able to: randomise schools; obtain parental consent for the use of data for research purposes; deliver the intervention adherently; ensure child attendance; complete child and teacher outcomes at scheduled times (0, 8 and 16 weeks), within a one month window for completion at each timepoint (i.e. between 6 and 10 weeks for the 8 week assessment and between 14 and 18 weeks for the 16 week assessment), with retention from baseline to follow-up. Secondary aims will be to estimate parameters for a sample size calculation for the subsequent larger trial, standardise our measures of adherence of teacher delivery, and validate our teacher-rated measure of classroom behaviour and child quiz.

The sample for the study will comprise consenting (n=360) children in ten schools.
Criteria for judging feasibility are as follows:

7.1.1 Randomising schools:

- Randomisation according to allocation without contamination for all ten schools

7.1.2 Parental and child consent:

- ≥ 60% of targeted parents (i.e. parents of children in participating classes) giving informed consent for data use (n=360, from 600)

7.1.3 Adherent delivery:

- Of the ten teachers delivering the intervention, at least eight achieving acceptable adherence ratings for an observed session

7.1.4 Outcome completion:

- ≥80% of children completing outcome measures and giving assent for these to be used for research (n=288, from 360).

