8.1 Design

The design will be a parallel group feasibility cluster RCT with random allocation of schools to one of two arms, in a 1:1 ratio.

The usual school curriculum will be delivered without interference in both conditions, with assessments at baseline (0-weeks), 8-weeks and 16-weeks (post intervention, primary endpoint) and a proposed primary outcome of emotional and behavioural problems for vulnerable children at 16-weeks. Waitlist control participants will be offered the intervention later in the term or the following school year. The intervention will be delivered to whole classes; each school will be two or three form entry, and thus comprise two or three classes. Each class will comprise around thirty children

PROTOCOL IDENTIFICATION Amendment number: Original V1 Issue date: 251021 Authors: [name] Amendment I 010322: Figures for feasibility amended to proportions; proportion of children giving baseline data added (as logical follow-on from parental consent/child assent rates).

Schools will be randomised to classes receiving CUES-Ed, in addition to the usual school curriculum, either now (CUES-Ed) or later (waitlist control, WL). The usual school curriculum is nationally set, with limited scope for variation by school. We will record what is delivered in the usual curriculum, but will not interfere with usual delivery. In particular, as CUES-Ed will not comprise additional hours of teaching, we will record any difference arising in the routine curriculum delivered in intervention and control schools.

Trained research workers will complete assessments with children and teachers at baseline (T0), 8-weeks (T1) and 16-weeks (T2, post therapy), see Figure 1.

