12.2 Secondary outcome measures

Parameter estimation to determine sample size for a full trial will be based on outcomes on the proposed primary clinical outcome measure, M&MF (see 12.3).

Validation of the classroom based outcome measure (see 12.3) will be done through psychometric testing of collected data and comparison of teacher ratings to an observer rating.

Teacher adherence ratings will be designed and tested during the pilot.

Child quiz data will be collected during the pilot. Stigma and appraisal components have been standardised (Underwood et al., in press): we will check current data follows the same pattern, and validate the remaining components of the quiz against the other study measures (M&MF, CORS, see 12.3).

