12.3 Proposed primary and secondary questionnaire outcome measures

- We plan to use the following instrument as the potential primary outcome for the future RCT, Me and My Feelings (Deighton et al., 2013). This comprises 16 items, each rated 0 (best) to 2 (worst), measuring emotional (M&MF-E) and behavioral (M&MF-B) difficulties (M&MF-E, ten items; borderline/clinical cut-off >9; M&MF-B, six items; borderline/clinical cut-off >5). The measure is designed specifically for use in schools to evaluate public health initiatives, and has been widely used with children of this age group.

Proposed secondary outcomes for the future RCT are:

- The Children's Outcome Rating Scale (CORS, Duncan, Miller & Sparks, 2003) measures wellbeing/distress across four items, each rated 0 (worst) to 10 (best); clinical cut-off <32. The measure is widely used with children of this age.
- Children complete a quiz assessing learning from CUES-Ed (see Appendix 1). The quiz has been completed by large numbers of children during in-service delivery of CUES-Ed, so is acceptable for completion, with face validity. We are in the process of establishing norms, and will validate the measure as part of this pilot study.
- Teachers complete a rating of whole class behaviour involving estimates of the proportion of the class displaying particular behaviours 'always' or 'never', with the remainder displaying the behaviour 'sometimes'. We will validate this measure as part of this pilot study (see Appendix 2).

In addition:

- *Teacher adherence* data will be collected from a checklist to be standardised during the study.

- *Child attendance* data will be collected from the class register

13. Participant timeline

The delivery timeline needs to fit school terms, so has been designed to accommodate breaks.

Week	Study phase	Activity
-6+	Pre-engagement	
 • Approach local authority
-4+	Engagement	
 • Approach headteachers. • As part of consent, heads check teacher availability. • Headteacher consent • Teacher consent
-3 to -2	Participation, pre-randomisation	
 • Letter, information sheet and consent sent to parents • Classes informed of study by teacher using video from research team
-1 to 0	Baseline	
 • Child assent • Child measures • Teacher measures
0	Randomisation	
 • Research team informs school of allocation

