20.4 Additional analyses

Psychometric analyses will be employed to validate the child quiz, teacher classroom ratings and teacher adherence rating. Vulnerable children will be identified as those scoring in the borderline or clinical range on either subscale of the M&MF.

21. Data monitoring

Data monitoring will be the responsibility of the study research lead [name], overseen by the trial management group and the steering committee. As data will be collected over a relatively short period of time, there will be no interim analyses. As we do not

anticipate risks to participant safety as a direct result of the study and will not be conducting any interim data analysis, we will not convene a separate Data Monitoring Committee, and will devolve these functions to the trial steering committee (TSC) which will be detailed in the TSC charter. The study will be subject to the standard local and national governance frameworks of SLaM R&D, CAMHS clinical services and research co-ordination, and our ethics committee.

The pilot study will be overseen by a steering committee comprising the research team, an education representative and a senior academic not directly involved in the study.

An independent steering committee will be established for the future, full trial.

22. Harms

We will ask teachers to report to the study team any concerns about CUES-Ed or the assessment protocol or any other aspect of the study, expressed by teachers themselves, parents, or children. These will be reviewed by the steering committee for severity, and attributability to the study in liaison with the school, and parents if relevant. Adverse events judged serious and attributed to participation in the study will be reported as below. We do not envisage, given the extensive delivery to date, without any adverse events, that these will be a frequent occurrence, or that an event will trigger cessation of the study.

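### The full trial's proposed primary outcome is in vulnerable children, but the only planned M&MF model, which should supply its sample-size parameters, is in all children

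*Protocol*

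**What the plan says.** **Target population.** Section 8.1 gives the full trial "a proposed primary outcome of emotional and behavioural problems for vulnerable children at 16-weeks". Section 7.1 states the aim of the later trial as effectiveness "in reducing emotional and behavioural problems in vulnerable Year 4 schoolchildren in England". Section 6.1.2 says that "vulnerable children within the class are the key target group for change", while expecting some benefit for all children.

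**Source of the parameters.** Section 12.2: "Parameter estimation to determine sample size for a full trial will be based on outcomes on the proposed primary clinical outcome measure, M&MF". The synopsis and sections 7.1 and 7.3 list this as a secondary objective.

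**Planned analysis.** Section 20.2: "The potential primary outcome the M&MF will be summarised using a mixed effects linear regression". The model has random effects for school and class, and baseline score, sex and age as fixed effects. It reports the between-group effect with its confidence interval and the ICC. Section 20.3 sets the primary population as all children with at least one post-baseline timepoint.

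**Definition of vulnerable.** Section 20.4: "Vulnerable children will be identified as those scoring in the borderline or clinical range on either subscale of the M&MF". No model, effect, SD, ICC or follow-up rate is attached to this definition. The cut-offs are in section 12.3: "M&MF-E, ten items; borderline/clinical cut-off >9; M&MF-B, six items; borderline/clinical cut-off >5", on items scored from 0 (best) to 2 (worst). The synopsis instead describes "vulnerable children (scoring at or below borderline/clinical cut-off) receiving the intervention in whole classes".

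**The concern.** One outcome has two populations. Where the full trial is described, the M&MF outcome belongs to vulnerable children; where the analysis is described, it belongs to every child with follow-up. The second version is the one that will produce numbers.

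What is at stake is one of the pilot's main products. A full trial analysed in vulnerable children needs their outcome SD, ICC, baseline-to-follow-up correlation, number per class and school, and retention. Estimates from whole classes do not supply these. The primary feasibility results (consent, assent, follow-up, adherence, fidelity) are not affected.

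**Working it through.** **Inputs.** From the service table in section 6.1.4: 28% above the M&MF-E cut-off (n = 144; SD 2.45 before, 3.33 after the programme) and 20% above the M&MF-B cut-off (n = 100). The implied cohorts, 144/0.28 = 514 and 100/0.20 = 500, agree within rounding. From section 14: 360 consenting children, 10 schools, two classes each, 80% follow-up, so 0.80 × 360 = 288. The ICC is not given; 0.01 to 0.10 is assumed.

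**The plan's own figure.** 1.96 × √(0.8 × 0.2/360) = 0.0413, which reproduces the stated ±4.1% for follow-up in all children (clustering ignored).

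**Share vulnerable on either subscale.** With full overlap it is max(28%, 20%) = 28%; with none it is 28% + 20% = 48%.

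**Numbers.**
- Baseline: 360 × 0.28 = 101 to 360 × 0.48 = 173.
- Followed up: 288 × 0.28 = 81 to 288 × 0.48 = 138.
- Per school: 8.06 to 13.82, against 28.8 for all children.
- Per class: 4.0 to 6.9, against 14.4.

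**Design effect**, 1 + (m − 1) × ICC, with m followed children per school:

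| Assumed ICC | All, m = 28.8 | Vulnerable, m = 8.06 | Vulnerable, m = 13.82 |
|---|---|---|---|
| 0.01 | 1.28 | 1.07 | 1.13 |
| 0.05 | 2.39 | 1.35 | 1.64 |
| 0.10 | 3.78 | 1.71 | 2.28 |

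At ICC 0.05 a school contributes 28.8/2.39 = 12.1 effective children in the whole-class analysis, but 8.06/1.353 = 6.0 to 13.82/1.641 = 8.4 effective vulnerable children. At equal effect, SD and ICC, a trial in vulnerable children would therefore need about 12.05/8.42 = 1.4 to 12.05/5.96 = 2.0 times the schools that whole-class figures suggest.

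**SD.** The whole-class SD is not given. Purely as an illustration, take normal M&MF-E scores with 28% above 9.5 and a mean of 11.9 among those. The standardised cut is 0.583 and the standardised tail mean 1.202, so SD = (11.9 − 9.5)/(1.202 − 0.583) = 3.9. This is rough: it implies a tail SD of 1.96, not the reported 2.45. It does show that the whole-class SD need not match 2.45 or 3.33.

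**Retention.** At 80% follow-up the half-width in vulnerable children is 1.96 × √(0.16/100.8) = 7.8 points to 1.96 × √(0.16/172.8) = 6.0 points before clustering, against 4.1 for all children.

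**Dilution, as an illustration.** Suppose benefit occurs only in vulnerable children, a share p of the class, and the SDs are equal. The whole-class difference is p times the target effect, so the number of children analysed rises by 1/p². Obtaining n vulnerable children already requires n/p children, so the like-for-like ratio in children recruited is 1/p: 1/0.48 = 2.1 to 1/0.28 = 3.6 before clustering. In schools at ICC 0.05 it is (1/p) × (2.39/design effect in vulnerable children): 2.083 × 2.39/1.641 = 3.0 to 3.571 × 2.39/1.353 = 6.3.

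**Synopsis direction.** Higher M&MF scores are worse, and the borderline/clinical range lies above 9 (E) or above 5 (B). Scores at the cut-off or lower are outside that range, so the synopsis reverses sections 12.3 and 20.4.

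**The case against.** **The SAP could settle it.** Section 20 promises a SAP before database lock, and a definition placed under additional analyses suggests that some analysis by vulnerability is intended. The absence of a detailed subgroup model would indeed be no finding. What remains is that sections 20.2 and 20.3 fix a population that disagrees with section 8.1, and a SAP that follows them carries the mismatch forward.

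**The protocol does not say that whole-class values will size the full trial.** True. But section 12.2 takes the parameters from the M&MF, and only one M&MF model is planned.

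**A reader might infer a 4- to 13-fold error in sample size** from 1/0.48² = 4.3 and 1/0.28² = 12.8. The documents do not support this. It assumes no benefit outside the vulnerable group, whereas section 6.1.2 expects some for all. It assumes equal SDs, and it compares a count of all children with a count of vulnerable children only. It also assumes that the pilot's observed effect would become the design effect size, which the protocol does not state.

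**A reader might infer that vulnerability will be set on a post-randomisation score**, because section 20.4 names no timepoint. That is speculative. Baseline M&MF is collected before randomisation, and the vulnerable groups in section 6.1.4 have pre-programme means above the cut-offs (11.9 and 7.43).

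**A reader might infer that the synopsis selects the wrong children.** It selects none: all Year 4 children are eligible. The phrase names no measure, and lower is worse on the CORS (cut-off below 32), so part of it fits that scale. It is a wording slip, although the synopsis line concerns emotional and behavioural problems, which the M&MF measures.

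**Subgroup estimates will be imprecise.** This stands, and is why the whole-class analysis should be kept.

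**Conclusion.** The mismatch is real and lies in the protocol's stated rules. As written, no planned analysis estimates the M&MF effect, SD or ICC in the population in which the full trial's primary outcome is proposed. The effect and ICC that are planned belong to a different population.

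The firmest part of the size is the number of children: 81 to 138 of 288, or 8 to 14 per school against 29. This rests on service data from in-person delivery, mainly in South London, and on unknown overlap between the subscales. The design-effect contrast (1.35 to 1.64 against 2.39) also rests on an assumed ICC of 0.05, taken as equal in both populations.

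The direction of the resulting error in the full-trial sample size cannot be fixed from the documents. Cluster size alone would make whole-class figures too optimistic about the number of schools; dilution of an effect confined to vulnerable children would make them too pessimistic. The dilution figure, about 2- to 4-fold in children recruited before clustering, is an illustration only. The synopsis wording is a minor correction.

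**What to change.** 1. In sections 20.2 and 20.4, state that the same mixed model is also fitted in children vulnerable at baseline, defined as M&MF-E >9 or M&MF-B >5 at T0.
2. For that group report the between-group effect with its interval, SD, ICC with its interval, baseline-to-16-week correlation, number per class and follow-up rate, alongside the whole-class results.
3. In section 12.2, state that the full trial will be sized on the vulnerable-group parameters, with the whole-class estimates as support.
4. Align the synopsis with sections 12.3 and 20.4: vulnerable means scoring in the borderline or clinical range.

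The cost is wording. Baseline M&MF is already collected, so no new data and no change in conduct are needed. The price is imprecision: with 10 schools and about 4 to 7 vulnerable children followed per class, intervals will be wide, above all for the ICC. The sizing should therefore use a range of ICC values, informed by the whole-class estimate, instead of a single point estimate.
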